3.4.2 Categorical Variables

For categorical variables such as gender, in-hospital event rates, and angina status, results within treatment arm will be summarized with subject counts and percentages. Differences between the two treatment arms, where specified, will be summarized with the difference in percentages, the asymptotic 95% confidence interval for the difference of two percentages, and a p-value based on a chi-squared test. If 20% or more of the expected cell frequencies are less than 5 then a Fisher's Exact test will be used to test for differences in proportions.

For the determination of event rates in-hospital, the number of all subjects in the patient patient population will be used as the denominator. For variables ascertained at follow-up such as angina status, the denominator will be only those subjects who had follow-up performed at that time point. Unless otherwise noted, subjects with missing data are excluded from the denominator.

For secondary analyses of any type of death event for which event rates will be calculated, the denominator will include only subjects who have either had the event, died prior to the event time of interest, or had sufficient follow-up to be declared eligible for the endpoint. Sufficient follow-up implies that the subject had a follow-up visit past the lower limit of the window for the analysis time point (-7 days for the 30 day endpoint, and -30 days for yearly endpoints). Formulas for calculating confidence intervals for the categorical variables are given below. Please note that in using these formulas, it is assumed that the data are independent and binomially distributed. For the confidence interval for the difference of two proportions, it is also assumed that the two samples are independent, the samples sizes for the two groups are large (≥ 20 per group), the expected event and non-event counts for both groups are at least 5, and the distribution is asymptotically normal.

1. $100(1-\alpha)$ % Confidence Interval For The Difference Of Two Proportions⁶

Lower Confidence Limit =
$$(\hat{p}_1 - \hat{p}_2) - Z_{\frac{\alpha}{2}} \sqrt{\left(\frac{\hat{p}_1 \hat{q}_1}{n_1} + \frac{\hat{p}_2 \hat{q}_2}{n_2}\right) + \frac{1}{2} \left(\frac{1}{n_1} + \frac{1}{n_2}\right)}$$

Upper Confidence Limit = $(\hat{p}_1 - \hat{p}_2) + Z_{\frac{\alpha}{2}} \sqrt{\left(\frac{\hat{p}_1 \hat{q}_1}{n_1} + \frac{\hat{p}_2 \hat{q}_2}{n_2}\right) + \frac{1}{2} \left(\frac{1}{n_1} + \frac{1}{n_2}\right)}$

where:

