3.4.4 Hypothesis Testing

Formal non-inferiority and superiority tests are planned for the primary and powered secondary endpoints. These endpoints are Kaplan-Meier failure rate estimates (higher rate is worse).

All non-inferiority tests will be one-sided. The null and alternative hypotheses will be of the following form (assuming showing A non-inferior to B):

 $\begin{array}{ll} H_0: \ Endpoint_A - Endpoint_B \geq \Delta \\ H_A: \ Endpoint_A - Endpoint_B < \Delta \end{array}$

For one-sided superiority test, the null and alternative hypotheses will be of the form (assuming showing A superior to B):

H₀: Endpoint $_{\rm A}$ – Endpoint $_{\rm B} \ge 0$ H_A: Endpoint $_{\rm A}$ – Endpoint $_{\rm B} < 0$

For two-sided superiority test, the null and alternative hypotheses will be of the form

H₀: Endpoint $_A$ – Endpoint $_B$ = 0 H_A: Endpoint $_A$ – Endpoint $_B \neq 0$

Methods for testing are as follows. Detailed specifications on non-inferiority deltas, significance levels, and decision rules are provided in the section on analysis of endpoints.

1. Test for non-inferiority

The test for non-inferiority will be based on the one-sided $(1-\alpha)$ confidence interval of the difference between the two treatment arms. If the upper bound of the one-sided $(1-\alpha)$ confidence interval is less than Δ , then it will be concluded that the null hypothesis can be rejected and non-inferiority will be declared.

2. Test for superiority

For one-sided superiority test, if the one-sided $(1-\alpha)$ confidence interval is less than 0, then it will be concluded that the null hypothesis can be rejected and superiority will be declared.

For two-sided superiority test, if the $(1-\alpha)$ confidence interval does not contain 0, then it will be concluded that the null hypothesis can be rejected and superiority will be declared.

Caution must be exercised when interpreting p-values displayed for analyses other than those performed for the primary and powered secondary endpoints, as the study was not powered to detect differences for any of those other variables. The resulting p-values, whether or not less-than 0.05, may be a result simply due to pure chance.

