3.7 FOLLOW-UP TIME POINTS

All subjects will have follow-up as a telephone contact or office visit at 30 ± 7 days, 180 ± 14 days, and at 1, 2, 3, 4 and 5 years (-30days/+60 days). Procedures and tests will be performed at each follow-up time point as per the Schedule of Events within the study protocol. Subjects who have not yet completed the 3-year visit (unless the most recent follow-up was completed within 28 days of the AE check initiation), or who completed the 3 year visit before the lower bound of the 28 day window (i.e. before 1067 days after randomization) will be followed up with a phone call or office visit prior to database snapshot to capture potential withdrawal dates and any events that may have occurred since the last visit. Events dates and early withdrawal date will be collected at this call.

Primary analyses for the study will take place when approximately 50% of the patients have reached the 3-year follow-up AND all patients have reached the 2-year follow-up, whichever time point is latest.

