3.8 HANDLING OF MISSING DATA

Every effort will be made to minimize the loss of subjects during this study. Subjects discontinuing early from the study and their reason for dropping out will be summarized by group to see if any biases in the analyses may have been created by any differences between groups.

The impact of missing data will be minimized in the analysis of the primary and key secondary endpoints by performing the analyses using Kaplan-Meier estimates, where subjects will be censored at their last assessed time point.

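### Disability 90 days after stroke: no rule counts patients who die before the assessment, so this descriptive severity summary would most naturally cover assessed survivors only

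*SAP*

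**What the plan says.** **The endpoint.** SAP 2.3.3 and protocol 5.2 and 9.1.3 list disability after a stroke, measured at 90 days ± 2 weeks, among the other (non-powered) secondary endpoints. Protocol 16.2 describes it as summarizing stroke severity on the mRS. Protocol 6.3 requires the mRS at that time after any adjudicated stroke. The scale in protocol 16.1.3 and the questionnaire in Appendix J both end at grade 5, and neither has a grade for death.

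**The denominator rules.** SAP 3.4.2 contains three:
- For variables ascertained at follow-up, with angina status as the example, "the denominator will be only those subjects who had follow-up performed at that time point".
- As a general default, "Unless otherwise noted, subjects with missing data are excluded from the denominator".
- For death-event rates only, the denominator keeps patients who had the event, "died prior to the event time of interest, or had sufficient follow-up to be declared eligible for the endpoint".

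The same section says: "Differences between the two treatment arms, where specified, will be summarized with the difference in percentages". Nothing there or in SAP 2.3.3 makes an exception for 90-day disability.

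**Missing data.** SAP 3.8 says "Subjects discontinuing early from the study and their reason for dropping out will be summarized by group". Its analysis rule, Kaplan-Meier estimation with censoring, has a limited reach: "The impact of missing data will be minimized in the analysis of the primary and key secondary endpoints". The worst-case imputation in protocol 17.5.1 is for quality-of-life scores.

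**The concern.** A severity measure should register the most severe outcomes. Patients who die of their stroke generally do so before day 90, so they cannot have the mRS on which the endpoint depends. If they simply leave the denominator, the table answers a narrower question: how disabled were the patients who lived to be assessed? An arm with several fatal strokes could look the same as an arm with none.

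The stakes are limited but not empty. The margin justification in SAP 2.6 relies partly on an expectation of fewer strokes with PCI, and ranks stroke above MI in clinical importance in most cases. Readers will therefore want to know how severe the strokes were in each arm.

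**Working it through.** **Step 1. Can a fatal stroke be in the set?** Yes. Protocol 16.1.3 requires four criteria for a stroke. Under the second, a deficit lasting less than 24 hours still qualifies if it leads to death. That clause only waives the duration requirement, and the other criteria, including specialist confirmation with imaging or lumbar puncture, must still be met. Fatal strokes can therefore qualify, though not on that clause alone. Protocol 16.1.1 places death due to stroke generally within 30 days, well before the 90-day assessment.

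**Step 2. Which rule applies to them?**
- The rule that keeps patients who died is confined to death-event rates.
- The follow-up-only rule applies by inference. The assessment is anchored to the stroke and is not one of the scheduled contacts, which are a telephone contact or "office visit at 30 ± 7 days, 180 ± 14 days, and at 1, 2, 3, 4 and 5 years".
- The general default remains, and no exception is noted. It leaves out a patient with no mRS.
- Neither document says whether the 90-day mRS is categorical or continuous. If it is continuous, SAP 3.4.1 summarizes the observations available and supplies no value for death. The result is again survivors only.

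**Step 3. How large could the understatement be?** There is no plan figure to reproduce, and the documents give no stroke fatality or disability rates. Both inputs below are assumptions, and the arithmetic presumes a disabled/not-disabled split that the plan does not define for this endpoint.

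Let f be the proportion of stroke patients who die before assessment and d the proportion of survivors who are disabled.

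- Survivors-only figure = d
- Dead or disabled per stroke = f + (1 − f) × d
- Shortfall = f × (1 − d)

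| d | f = 10% | f = 20% | f = 30% |
|---|---|---|---|
| 30% | 37% (7 points) | 44% (14 points) | 51% (21 points) |
| 50% | 55% (5 points) | 60% (10 points) | 65% (15 points) |
| 70% | 73% (3 points) | 76% (6 points) | 79% (9 points) |

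Each cell gives dead or disabled per stroke, with the shortfall of the survivors-only figure in parentheses. The range runs from 0.10 × 0.30 = 3 points to 0.30 × 0.70 = 21 points.

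**Step 4. What if a reader compares the arms?**
- With equal fatality, the survivors-only difference is 1/(1 − f) times the per-stroke difference: 1.11, 1.25 or 1.43 at 10%, 20% or 30% fatality. Direction is kept.
- With unequal fatality, a difference can be hidden. If 40% of survivors are disabled in both arms but fatality is 10% in one and 30% in the other, the survivors-only figures are equal. Per stroke they are 0.10 + 0.90 × 0.40 = 46% and 0.30 + 0.70 × 0.40 = 58%.

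**Step 5. How many patients?** As a rough scale only, take the 3-year stroke rates in protocol Table 2-2 (3.3% CABG, 0.9% PCI). They come from a post hoc subgroup treated with an earlier stent. Applied to 950 per arm:
- CABG: 950 × 0.033 ≈ 31 strokes, of which 10% to 30% is about 3 to 9 patients.
- PCI: 950 × 0.009 ≈ 9 strokes, of which 10% to 30% is about 1 to 3 patients.

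With 9 strokes and 10% fatality, the chance of no PCI death before assessment is 0.9⁹ ≈ 0.39 if deaths are independent. An arm with no such death is quite possible.

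**The case against.** **The reading is an inference.** SAP 3.4.2 excludes patients with missing data, but does not say that a patient who has died counts as missing on a disability scale. Protocol 17.5.1 does name death as a cause of missing data, but only for quality of life. The table mockups to which the SAP refers are not in the documents and may hold a rule. This stands: survivors-only is the most natural reading of the text, not a stated instruction.

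**Disability among survivors is a legitimate summary.** The endpoint is named for disability, on a scale the trial defines as 0 to 5, and deaths and strokes are reported elsewhere. This stands in part. The protocol nonetheless presents the measure as one of severity, and no endpoint listed in SAP 2.3.3 shows deaths among stroke patients, so a reader cannot easily put the two together.

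**Nothing depends on it.** The endpoint is outside the testing sequence in SAP 3.10. SAP 3.4 assigns a nominal two-sided 0.05 to non-powered endpoints, but protocol 9.1.7.2 treats p-values for other endpoints as descriptive, and SAP 3.4.4 warns: "Caution must be exercised when interpreting p-values displayed for analyses other than those performed for the primary and powered secondary endpoints". This stands, and it sets the grade.

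**Stronger readings that the documents do not support.**
- A reader might infer that severity is understated in both arms. That needs a death before assessment in each arm, and Step 5 shows that the PCI arm may have none.
- A reader might infer that the treatment comparison on disability would be distorted or reversed. SAP 3.4.2 gives arm differences only where specified, and none is specified for this endpoint. Reversal would also need unequal fatality together with less disability among survivors in the deadlier arm.
- A reader might infer that fatal strokes are lost from the main results. Any death counts in the primary composite, and all strokes and all deaths are reported in their own right.

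**Conclusion.** The gap is real and minor. No visible text says how patients who die before the 90-day mRS are counted. The stated defaults most naturally leave a summary of assessed survivors, whether the mRS is treated as categorical or continuous. That understates stroke severity in any arm with such a death.

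The size cannot be derived from the documents. The 3 to 21 point range rests entirely on assumed fatality of 10% to 30%, assumed disability of 30% to 70% among survivors, and an assumed binary split. The conclusion about the text also assumes that the unseen table mockups contain no rule for these deaths. The primary, powered, all-stroke and mortality results, and the testing sequence, are unaffected.

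**What to change.** In SAP 2.3.3 and 3.4.2, exempt this endpoint from the missing-data default and specify one table by arm, with all patients who had an adjudicated stroke as the denominator:
- mRS grades 0 to 5 at 90 days ± 2 weeks;
- death before the assessment as a separate worst category (grade 6), with stroke and non-stroke deaths shown separately;
- patients alive but not assessed, in their own row.

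Keep it descriptive, without a between-arm test, because the table conditions on an event after randomization. List the change in SAP section 5.

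The cost is a few lines of SAP text. Stroke dates, adjudicated causes of death and mRS scores are already collected. The downside is a small departure from the protocol's 0 to 5 scale. Grade 6 will also include some deaths unrelated to the stroke, which is why the two kinds are shown apart.

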9. STATISTICAL DESIGN AND ANALYSIS

This section describes the statistical considerations and analysis plans for the EXCEL trial. The study is powered for both the primary and the 2 major secondary endpoints through an anticipated median follow-up of three years.

In general, binary variables will be summarized using counts, percentages, and exact 95% confidence intervals. For continuous variables, percentiles, means, standard deviations, and 95% confidence intervals for the mean using the Gaussian approximation will be calculated. Time to event data will be summarized using Kaplan-Meier estimates and 95% confidence intervals. Kaplan-Meier curves will be constructed for the primary and major secondary endpoints and differences in treatment will be tested using the difference in Kaplan-Meier failure rates on all available data through 3-year follow-up at the time of the analysis (event driven analysis). All primary analyses will be measured from randomization onward and will be by intention to treat according to randomized assignment, regardless of what therapy was actually received. A sensitivity analysis will be performed on the primary endpoint defined from the index procedure date. The composite of all-cause mortality, MI, stroke (mRS \geq 1 and increase by \geq 1 from baseline), or unplanned revascularization for ischemia at 3 years post randomization will also be classified as a sensitivity analysis. Secondary analyses will be performed for the per protocol (PP) population (see also Section 9.1.5.2).

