9.1.3. Other Secondary Endpoints

The primary endpoint composite event rate (all-cause death, MI or stroke) and powered secondary endpoints at all time points other than median of 3 years will be analyzed as other secondary endpoints.

Time points for all other secondary endpoints, unless specified otherwise, are in-hospital, 30 and 180 days, 1, 2, 3, 4 and 5 years post-procedure.

Survival analysis techniques will be used to analyze the time-to-event variables. All of these analyses will be performed for these endpoints with time defined from date of randomization and (as a sensitivity analysis) from date of index procedure.

The other secondary endpoints are:

- All-cause mortality
 - Cardiac death
 - Non-cardiac death
- All myocardial infarctions (periprocedural, spontaneous, Q-wave and non Q-wave) including large and small MIs
- Protocol-defined MI
- MI adjudicated per Universal Definition
- Protocol-defined stroke

- All stroke (all, ischemic and hemorrhagic)
- Disability following stroke event at 90 days± 2 weeks
- Ischemia-driven revascularization
 - Ischemia-driven target lesion revascularization (TLR)
 - Ischemia-driven target vessel revascularization (TVR)
 - Ischemia-driven non target vessel revascularization (Non-TVR)
- All revascularization (ischemia driven and non-ischemia driven)
 - All target lesion revascularization (TLR)
 - All target vessel revascularization (TVR)
 - All non target vessel revascularization (non-TVR)
- Complete revascularization at baseline procedure, anatomic and functional (see Section 19. Appendix D)
- Stent thrombosis (ARC definition) symptomatic or asymptomatic
- Symptomatic graft stenosis or occlusion (since this requires angiographic documentation, this endpoint will be compared to symptomatic ARC definite stent thrombosis)
- Requirement for blood product transfusion
- Bleeding complications
 - Requirement for blood product transfusion
 - TIMI scale (major or minor)
 - BARC scale
- Time from randomization to procedure; time from procedure to discharge; ICU days; time from procedure to return to work
- Major adverse events (MAE) defined as composite of the following components. MAE will be assessed in-hospital and at 30 days only.
 - death
 - myocardial infarction
 - stroke
 - transfusion of ≥ 2 units of blood
 - TIMI major or minor bleeding
 - major arrhythmia
 - unplanned coronary revascularization for ischemia
 - any unplanned surgery or therapeutic radiologic procedure
 - renal failure

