2.3 DESIGN OF THE STUDY

The randomized control portion of this study (that will be referred to as RCT) is a prospective, unblinded, randomized multicenter trial of approximately 1,900 subjects enrolled at approximately 165 US and OUS centers. Following diagnostic angiography demonstrating significant ULMCA disease and consensus of the local Heart Team (qualified participating interventional cardiologist and cardiac surgeon) that the subject meets the study entry criteria, subjects will be consented and randomized 1:1 to: a) PCI using XIENCE (N=950), or b) CABG (N=950). Follow-up for all randomized subjects will continue for five years with a potential for additional follow-up to 10 years. The primary endpoint will be assessed at least 2-years after the last subject is randomized, with a median follow-up duration in all subjects of at least 3 years.

All randomized subjects will have a follow-up telephone contact or office visit at 30 days, 180 days, and 1, 2, 3, 4 and 5 years following the index procedure. In addition, to minimize bias in the assessment of the primary endpoint, at the time the last randomized subject reaches the 2-year follow-up duration (730 + 28 = 758 days), an additional adverse event (AE) check will be performed in order for data up to 3 years (365 days*3=1095 days) from the date of randomization to be collected equally in both arms.

The AE check will commence the day after the 2-year follow-up duration of the last subject enrolled (i.e. 758 days), and will be completed prior to the database snapshot. At this time,

subjects with either of the following conditions should be contacted by each clinical site by phone or office visit to collect AE information:

- Subjects who have not yet completed the 3-year visit, unless the most recent follow-up was completed within 28 days of the AE check initiation; or
- Subjects who have completed a 3-year visit before day 1067 after randomization (i.e. >28 days prior to exactly 3 years [1095 days]).

For subjects who have completed any follow-up visit at \geq (1095 – 28= 1067) days, the AE check is not required.

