2.3.3 Other Secondary Endpoints

The following additional endpoints will be analyzed:

- The endpoint of all-cause death, myocardial infarction or stroke, in-hospital, at 30 days, 180 days, and at 1, 2, 4 and 5 years.
- The endpoint of all-cause death, myocardial infarction, stroke or unplanned revascularization for ischemia in-hospital, at 30 days, 180 days, and 1, 2, 4 and 5 years.
- All cause mortality, cardiac death and non-cardiac death in-hospital, at 30 days, 180 days, and 1, 2, 3, 4 and 5 years.
- Protocol-defined MI at 30 days, 180 days, and 1, 2, 3, 4 and 5 years.
- All MI (periprocedural, spontaneous, Q-wave, and non Q-wave) at 30 days, 180 days, and 1, 2, 3, 4 and 5 years.
- MI adjudicated per Universal MI definition at 30 days, 180 days, and 1, 2, 3, 4 and 5 years.
- Protocol-defined stroke at 30 days, 180 days, and 1, 2, 3, 4 and 5 years.
- All stroke, ischemic stroke, and hemorrhagic stroke in-hospital, at 30 days, 180 days, and 1, 2, 3, 4 and 5 years.
- Disability following stroke event at 90 days± 2 weeks
- Complete revascularization at baseline procedure, anatomic and functional
- Ischemia-driven revascularization in-hospital, at 30 days, 180 days, and 1, 2, 3, 4 and 5 years.
 - All Ischemia-driven repeat revascularization procedures.
 - Ischemia-driven target lesion revascularization (TLR)
 - Ischemia-driven target vessel revascularization (TVR)
 - Ischemia-driven non target vessel revascularization (Non-TVR)

- All revascularization (ischemia driven and non-ischemia driven) at index procedure, in-hospital, at 30 days, 180 days, and 1, 2, 3, 4 and 5 years.
 - All repeat revascularization procedures
 - o All TLR
 - o All TVR
 - All non-TVR
- Stent thrombosis (ARC definition) symptomatic or asymptomatic PCI arm only inhospital, at 30 days, 180 days, and 1, 2, 3, 4 and 5 years.
- Symptomatic graft stenosis or occlusion (since this requires angiographic documentation, this endpoint will be compared to symptomatic ARC definite stent thrombosis) CABG arm only in-hospital, at 30 days, 180 days, and 1, 2, 3, 4 and 5 years.
- Bleeding complications at 30 days, 180 days, and 1, 2, 3, 4 and 5 years.
 - Requirement for blood product transfusion
 - TIMI scale (major or minor)
 - BARC scale
- Time from randomization to procedure; time from index procedure to discharge; ICU days; time from index procedure to return to work

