3.4.3 Time to Event Variables

Survival analysis techniques will be used to analyze the time-to-event variables that occur at or after 30 days of follow-up. All of these analyses will be performed with time defined from date of randomization and from date of procedure. Subjects without events will be censored at their last known event-free time point. If this event-free time point occurs after the analysis time point, the days to event variable will be set equal to the analysis time point so that the patient will be included in the analysis (e.g. if the last data point was collected at 3 years and 1 week post randomization, for the 3 year analysis, this patient is censored at exactly 3 years [1095 days]). For patients who did not have an event or early withdrawal and have not yet completed the 3 year visit, they will be censored at the time of their last follow-up. Time to first event curves will be constructed using Kaplan-Meier estimates.

For time to event variables such as MI, stroke and and revascularization, at all post discharge results will be summarized with Kaplan-Meier estimates of event rates. For time to event variables such as death and composite endpoints including death, deaths will be included for patients who dropped out early, but had a known death date, prior to study day 1095, from the national death registry.

For time to event analyses, hazard ratios, confidence interval for the hazard ratios, and p-values may also be presented from a Cox proportional hazards model.

Formulas are given below. Please note that in using these formulas, it is assumed that the data are independent observations.

The Kaplan-Meier product-limit estimator is defined as follows:

$$\hat{S}(T) = \begin{cases} 1 & \text{if } T_{\min} > T \\ \prod_{A \le T_i \le T} \left[1 - \frac{d_i}{r_i} \right] & \text{if } T_{\min} \le T. \end{cases}$$

The variance of S(T) is estimated by Greenwood's formula where

$$\hat{V}\left[\hat{S}(T)\right] = \hat{S}(T)^2 \sum_{A \le Ti \le T} \frac{d_i}{r_i(r_i - d_i)}$$

The Kaplan-Meier failure rate estimator and it's variance are defined as

$$\hat{F}(T) = 1 - \hat{S}(T)$$
$$\hat{V}[\hat{F}(T)] = \hat{V}[\hat{S}(T)]$$

 $100(1-\alpha)$ % Confidence Interval for the hazard ratio

Cox proportional hazards regression will be used to obtain the confidence interval for the hazard ratio. The phreg procedure in SAS will be used to obtain the Wald confidence limits. An example of the code is as follows:

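### SAP 3.4.2 keeps every death but drops survivors who have not reached the time point, and nothing says that the Kaplan-Meier rule in 3.4.3 governs death instead

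*SAP*

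**What the plan says.** SAP 2.3.3 lists among the secondary endpoints "All cause mortality, cardiac death and non-cardiac death in-hospital, at 30 days, 180 days, and 1, 2, 3, 4 and 5 years". Two SAP sections then describe how such rates are computed.

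- **SAP 3.4.2 (Categorical Variables)** has a rule specific to death rates in secondary analyses: "the denominator will include only subjects who have either had the event, died prior to the event time of interest, or had sufficient follow-up". Adequate follow-up means a visit past the lower window limit, given as minus "7 days for the 30 day endpoint, and -30 days for yearly endpoints". At 3 years that is day 1095 - 30 = 1065.
- **SAP 3.4.3 (Time to Event Variables)** says: "Survival analysis techniques will be used to analyze the time-to-event variables that occur at or after 30 days of follow-up". It names death as such a variable. Subjects without an event or early withdrawal who "have not yet completed the 3 year visit, they will be censored at the time of their last follow-up". However, its sentence prescribing Kaplan-Meier summaries of event rates gives MI, stroke and revascularization as examples, not death.

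The protocol points the same way as 3.4.3. Section 9 says "Time to event data will be summarized using Kaplan-Meier estimates and 95% confidence intervals", and section 9.1.3 says "Survival analysis techniques will be used to analyze the time-to-event variables".

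On timing, the primary analysis takes place once about half of the subjects have reached 3 years and all have reached 2 years (SAP 3.7). SAP 2.3 places the additional adverse event check "at the time the last randomized subject reaches the 2-year follow-up duration (730 + 28 = 758 days") and requires it to be finished before the database snapshot.

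**The concern.** The two rules treat the same subject differently. Take two subjects randomized on the same day, about 2.6 years before the cut. One died at 2.5 years and the other is alive. Under 3.4.2 the first enters both numerator and denominator, and the second enters neither. Under 3.4.3 the second contributes follow-up until censored. At a cut where many subjects are still short of 3 years, the first rule overstates the death rate and the second does not, given non-informative censoring.

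The SAP does not choose between them:

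- The 3.4.2 rule cannot be confined to in-hospital death. In-hospital rates have their own all-subjects denominator in the preceding paragraph, and 30-day and yearly windows have no meaning in hospital.
- SAP section 5 moves only the 30-day primary composite from a crude rate to Kaplan-Meier.
- SAP 3.8 applies censoring only to the primary and key secondary endpoints.
- Appendix A promises the endpoint components for the IFU without naming a method.

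At stake is the displayed absolute mortality in each arm, and the absolute difference, in an unblinded trial where death is the gravest component of the primary endpoint.

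**Working it through.** The plan gives no figure for a 3-year death rate under either rule, so there is nothing of its own to reproduce. The check compares the 3.4.2 rate with the true 3-year rate, which is the Kaplan-Meier target.

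**Inputs**
- Accrual 29 months (about 883 days), and loss of 8% at 3 years: SAP 2.5.1. Loss of 0% is run as well.
- Earliest cut, day 758 after last entry: SAP 2.3. Later cuts at days 788, 818 and 848 are assumptions.
- Three-year death of 9.0% (CABG) and 3.7% (stent): Protocol Table 2-2. The value of 7% is illustrative.
- Further assumptions: uniform accrual, constant hazards of death and loss, and contact at the cut date counted as follow-up.

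With the 2-year minimum, uniform accrual gives a median follow-up of 24 + 14.5 = 38.5 months, in line with the plan's figure of about 3 years.

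**Formula.** Let c be a subject's follow-up time at the cut and u = min(c, 1095). Then rate under 3.4.2 = D / (D + S), where D is the share observed to die by u and S is the share alive and followed to at least day 1065. The daily death hazard is λ = -ln(1 - p)/1095.

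**By hand: true rate 7%, no loss, cut at day 758.** Follow-up runs uniformly from 758 to 758 + 883 = 1641 days, and λ = 0.07257/1095 = 0.0000663.
- Past day 1095: (1641 - 1095)/883 = 61.8%, with death probability 0.0700.
- Short of day 1095: 38.2%, with mean follow-up (758 + 1095)/2 = 926.5 days and death probability 1 - exp(-0.0614) = 0.0596.
- D = 0.618 × 0.0700 + 0.382 × 0.0596 = 0.0660, so about 94% of all 3-year deaths are already seen.
- Past day 1065: (1641 - 1065)/883 = 65.2%, so S = 0.652 × 0.93 = 0.606.
- Rate = 0.0660/(0.0660 + 0.606) = 9.8%, against a true 7.0%.

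**Same case, cut at day 848.** Follow-up runs from 848 to 1731 days.
- 72.0% are past day 1095. The other 28.0% have mean follow-up 971.5 days and death probability 0.0624.
- D = 0.720 × 0.0700 + 0.280 × 0.0624 = 0.0679.
- S = (1731 - 1065)/883 × 0.93 = 0.754 × 0.93 = 0.701.
- Rate = 0.0679/0.769 = 8.8%.

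**With 8% loss**, numerical integration gives D = 0.0635 and S = 0.559 at day 758, so the rate is 0.0635/0.6228 = 10.2%. At day 848, D = 0.0652 and S = 0.647, so the rate is 9.2%.

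**Relative overstatement over true rates of 3.7-9%**

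| Cut (days after last entry) | No loss | 8% loss |
|---|---|---|
| 758 | 39-42% | 44-48% |
| 788 | 34-37% | 39-42% |
| 818 | 30-32% | 35-37% |
| 848 | 25-27% | 30-32% |

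At day 758, 32-34% of subjects leave the denominator without loss and 37-39% with loss. All of them are event-free.

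**Between arms, using the Table 2-2 rates.** The true difference is 9.0 - 3.7 = 5.3 points.
- Day 758: 12.52 - 5.26 = 7.3 points without loss, and 12.99 - 5.47 = 7.5 with loss.
- Day 848: 11.28 - 4.70 = 6.6 without loss, and 11.70 - 4.89 = 6.8 with loss.
- The ratio moves only from 3.7/9.0 = 0.41 to about 0.42.
- With 950 per arm, 8% loss and the day-758 cut, z is 4.51 under 3.4.2 and 4.48 under Kaplan-Meier.

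**Other time points.** Two-year death at the primary cut is inflated only through loss, by about 2.5% relative. Once all subjects have passed 3 years, the overstatement is nil without loss. With 8% loss it is about 4%, or about 8% if registry deaths of dropouts are added, as SAP 3.4.3 provides.

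**The case against.** The strongest reply is that the documents already point to Kaplan-Meier. SAP 3.4.3 calls death a time-to-event variable, covers everything from 30 days on and addresses subjects short of the 3-year visit. Protocol 9 and 9.1.3 agree. SAP 3.4.2 sits under a heading for categorical data. On this view the denominator rule is leftover wording, not a plan to use a biased estimator. That stands as to the likely intent, and it makes the harm conditional. It does not remove the conflict: the 3.4.2 rule is the more specific text on death rates, and a programmer following it would be following the SAP.

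Nor does any section tie the unpowered death rates to the primary cut. That also stands. The overstatement needs both conditions.

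Three stronger readings are tempting but not supported.

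- **A larger bias.** A cut exactly 24 months after last entry gives 44-54% under uniform accrual, and 60-73% if accrual is skewed late so that exactly half have reached 3 years. SAP 2.3 excludes that cut: the adverse event check starts only after day 758 and must finish before the snapshot. Day 758 is therefore the earliest date, and later cuts give less.
- **A biased primary result.** The primary and powered secondary endpoints are specified as Kaplan-Meier estimates and do not use the 3.4.2 denominator.
- **A missing 180-day window.** The sentence in 3.4.2 omits it, but SAP 3.7 defines it as 180 ± 14 days.

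**Conclusion.** The concern holds as an unresolved conflict between two SAP rules, one of which is biased at an immature cut. If 3-year death is reported under 3.4.2 at the primary cut, absolute rates and the absolute difference between arms are overstated by about 39-48% at day 758, falling to about 25-32% at day 848. The main uncertainty is the accrual pattern: the documents give its length but not its shape, and late-weighted accrual would raise these figures while early-weighted accrual would lower them. The part due to staggered entry disappears once every subject has passed 3 years.

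The consequence is confined to displayed absolute mortality for unpowered endpoints and, if the rule is used there, the Appendix A components. Study success is not in question. The change is worth making because the same data could be reported as roughly 7% or roughly 9-10% mortality, both within the wording of the SAP.

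**What to change.** - **SAP 3.4.2:** delete the death-denominator rule. In-hospital rates remain covered by the all-subjects denominator. If a crude proportion is still wanted, limit it to time points that every subject has passed.
- **SAP 3.4.3:** add one sentence stating that Kaplan-Meier with censoring governs all-cause, cardiac and non-cardiac death from 30 days onward, including the components reported under Appendix A.

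The cost is about two sentences of SAP text. No new data are needed and the powered tests do not change.

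There is one small trade-off. The 3.4.2 rule keeps deaths from other causes in the denominator, whereas Kaplan-Meier for cardiac death censors them. With 4% cardiac and 3% non-cardiac death, Kaplan-Meier gives 1 - exp[(4/7) × ln 0.93] = 4.06%, an excess of 0.06 points. A cumulative incidence estimate for cause-specific death would remove it.
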